### **Date of Last Dose of Study Treatment**

No imputation will be done for first dose date. Date of last dose of study treatment, if unknown or partially unknown, will be imputed as follows:

- If the last date of study treatment is completely missing and there is no Disposition CRF page for the treatment phase and no death date, the patient should be considered to be ongoing and use the data cutoff date for the analysis as the last dosing date; or
- If the last date of study treatment is completely or partially missing and there is EITHER a Disposition CRF page for the treatment phase OR a death date available (on or prior to the data cutoff date), then impute this date as the last dose date:
  - = 31DECYYYY, if only Year is available and Year < Year of min (Date of Completion/Discontinuation from the Disposition CRF page for the treatment phase, death date),
  - = Last day of the month, if both Year and Month are available and Year = Year of min (Date of Completion/Discontinuation from the Disposition CRF page for the treatment phase, death date) and Month < the month of min (Date of Completion/Discontinuation from the Disposition CRF page for the treatment phase, death date), or
  - = min (Date of Completion/Discontinuation from the Disposition CRF page for the treatment phase, death date), for all other cases.

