8.3.1. Time Period and Frequency for Collecting AE and SAE Information

The time period for actively eliciting and collecting AEs and SAEs (“active collection period”) for each participant begins from the time the participant provides informed consent, which is obtained before the participant’s participation in the study (ie, before undergoing any study-related procedure and/or receiving study intervention), through and including a minimum of 28 calendar days after the last administration of the study intervention.

Follow-up by the investigator continues throughout and after the active collection period and until the AE or SAE or its sequelae resolve or stabilize at a level acceptable to the investigator and Pfizer concurs with that assessment.

For participants who are screen failures, the active collection period ends when screen failure status is determined.

If the participant withdraws from the study and also withdraws consent for the collection of future information, the active collection period ends when consent is withdrawn.

If a participant definitively discontinues or temporarily discontinues study intervention because of an AE or SAE, the AE or SAE must be recorded on the CRF and the SAE reported using the CT SAE Report Form.

Investigators are not obligated to actively seek AEs or SAEs after the participant has concluded study participation. However, if the investigator learns of any SAE, including a death, at any time after a participant has completed the study, and he/she considers the event to be reasonably related to the study intervention, the investigator must promptly report the SAE to Pfizer using the CT SAE Report Form.

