#### **3.3. Safety Endpoints**

Safety endpoints will be summarized based on the on-treatment period unless otherwise specified.

On-treatment is defined as the time from the first non-zero dose of study treatment to the last non-zero dose + 28 days.

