#### **Other Missing or Partial Dates**

Imputation methods for other partial dates are as follows:

- If the day of the month is missing for a start date used in a calculation, the first day of the month will be used to replace the missing date.
- If both the day and month are missing for a start date, the first day of the year is used.
- For stop dates, the last day of the month, or last day of the year is used if the day or day and month are missing, respectively.
- If the date is completely missing, no imputation will be performed.

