#### **6.2.3.1. Exposure to Glasdegib**

The summary of treatment exposure for glasdegib will include the following information:

- Treatment duration (weeks).

The duration of glasdegib (in weeks) is defined as:

$$\text{Treatment duration (weeks)} = (\text{last dose date} - \text{first dose date} + 1)/7.$$

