### **6.2.3.5. Exposure to Azacitidine (Non-intensive Study Only)**

The summary of treatment exposure for azacitidine will include the following information:

- Treatment duration (weeks).

Azacitidine is administered by subcutaneous injection (SC) or intravenous (IV) infusion 75 mg/m^2 daily for 7 days, in 28 day cycles.

The dose level for azacitidine captured in the CRF is calculated as actual dose administered/body surface area (BSA) (mg/m^2). The last available weight of the patient on or prior to the day of dosing will be used.

The duration of azacitidine (in weeks) during the study for a patient is defined as:

$$\text{Treatment duration (weeks)} = (\text{last dose date} - \text{first dose date} + 1)/7.$$

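### The last-dose imputation rule mishandles a known month in an earlier calendar year and returns a date after the month the site recorded

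*SAP*

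**What the plan says.** SAP 5.3.1, under Date of Last Dose of Study Treatment, applies when the date is completely or partly missing and there is a treatment-phase disposition page or a death date. Call the earlier of those two dates the reference date. Three rules follow:

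1. Year only: "31DECYYYY, if only Year is available and Year < Year of min" of the two dates.
2. Year and month: "Last day of the month, if both Year and Month are available and Year = Year of min" of the two dates, with the additional condition that the recorded month precedes the reference month.
3. Everything else: "min (Date of Completion/Discontinuation from the Disposition CRF page for the treatment phase, death date), for all other cases".

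For other partial dates, the same section has a simpler convention with no same-year condition: "For stop dates, the last day of the month, or last day of the year is used".

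The last-dose date feeds several derived quantities:

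- treatment duration for glasdegib (SAP 6.2.3.1) and azacitidine (SAP 6.2.3.5), each last dose minus first dose plus one, divided by 7;
- treatment duration as a planned statistic in Protocol 9.4.1;
- the length of the last cycle (SAP 5.2.3);
- the safety window in SAP 3.3: "On-treatment is defined as the time from the first non-zero dose of study treatment to the last non-zero dose + 28 days".

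**The concern.** Rule 2 requires the recorded year to equal the reference year, so it stops working once treatment-phase disposition or death falls in the following calendar year. Such a record has a known month, so rule 1 does not apply either. Rule 3 then supplies the reference date, which contradicts what the site wrote down.

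The result is also perverse in terms of information: a site that records the month gets a later imputed date than a site that records only the year. The error is always upward.

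Treatment duration is the quantity chiefly at stake, because it is the only item listed in each drug's exposure summary. The on-treatment window can also be stretched. Adverse event counts would rarely follow, since routine collection runs "through and including a minimum of 28 calendar days after the last administration of the study intervention" and that period fits inside the window counted from month end. A count changes only if an event beyond that period is on record, for example a related serious event that the investigator learns of later (Protocol 8.3.1).

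**Working it through.** The plan states no figure here to reproduce, so the check applies the three rules literally to dates.

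**Inputs.** The rules are from SAP 5.3.1, the duration formulas from SAP 6.2.3.1 and 6.2.3.5, and the 28-day window from SAP 3.3. The maxima of 34 participants (B1371019) and 3 (B1371012) are from SAP 2.2. Calendar dates, lags, the partial-date rate and an arm size of 17 are assumptions.

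**Step 1: examples.**

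| Recorded last dose | Reference date | Rule that applies | Imputed date | Days past recorded month |
|---|---|---|---|---|
| Nov 2021 | 10 Dec 2021 | 2 | 30 Nov 2021 | 0 |
| Nov 2021 | 10 Jan 2022 | 3 | 10 Jan 2022 | 41 |
| Dec 2021 | 20 Jan 2022 | 3 | 20 Jan 2022 | 20 |
| 2021 only | 10 Jan 2022 | 1 | 31 Dec 2021 | not applicable |

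The excesses are 41/7 = 5.9 weeks and 20/7 = 2.9 weeks. In the second row the on-treatment window ends on 10 January + 28 days = 7 February 2022. Counted from month end it would end on 30 November + 28 days = 28 December 2021.

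**Step 2: is it general?** The rules were run for every reference date from 1 January 2022 to 31 December 2023, with every recorded month from March 2021 up to the reference month. All 11,680 combinations with an earlier recorded year were imputed after the recorded month, by at least 1 day. None of the 4,764 same-year combinations was. These counts show only that the fault is systematic, not how common it is.

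**Step 3: how often?** Suppose last doses are spread evenly over a year and the reference date follows by a fixed lag of L days. For the lags below, the fault occurs when the last dose falls in the final L days of December.

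- Share of month-known partial dates affected = L/365: 7/365 = 1.9%, 14/365 = 3.8%, 28/365 = 7.7%.
- The excess past month end runs from 1 to L days, so its mean is (L + 1)/2: 4, 7.5 and 14.5 days.
- At L = 0 nothing is affected.

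If 5–10% of 37 participants have a month-known partial date and L = 28, the expected number affected is 37 × 0.05 × 28/365 = 0.14 to 37 × 0.10 × 28/365 = 0.28.

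**Step 4: effect on mean duration, given one affected record.** Shift in weeks = excess days / 7 / N.

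| N | 14.5 days | 20 days | 41 days |
|---|---|---|---|
| 34 | 0.06 | 0.08 | 0.17 |
| 17 (assumed arm) | 0.12 | 0.17 | 0.34 |
| 3 (B1371012) | 0.69 | 0.95 | 1.95 |

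**The case against.** The gap in the wording is hard to dispute; the case on the other side is that it will hardly matter.

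- **Size.** The 41-day example implies a lag of 41 to 70 days from last dose to disposition, longer than any lag in step 3. At a 28-day lag, the 14.5-day column is the typical one. This stands, and the larger shifts should be read as conditional on one such record. For B1371012 the expected number affected is only 3 × 0.05 × 7.7% = 0.012 to 3 × 0.10 × 7.7% = 0.023.
- **Partial dates may be rare.** Dosing is recorded on the CRF, there is a dosing diary and tablet counts, and monitors verify source data. This also stands: the 5–10% is an assumption, and zero affected participants is the most likely outcome. A nonzero lag is plausible, however. Azacitidine is given on Days 1–7 of a 28-day cycle, so discontinuing at the next Day 1 visit puts disposition about 29 − 7 = 22 days after the last dose.
- **Another source may govern.** SAP 5.3 says a CDISC rulebook will be followed for partial dates. Its content is not in the documents, so it cannot be assumed to override an explicit study-specific rule. The month-end convention for other dates does not rescue the case either, because last dose has its own rule.
- **The link to duration is inferred.** The imputation concerns the last dose of any study drug (SAP 3.2), while the SAP durations are per drug, and the SAP does not say that the imputation is applied drug by drug. This is a fair caveat. Still, Protocol 9.4.1 plans a treatment duration from the last dose date, and no other last-dose imputation is given.
- **The case is not undefined.** This is true: the catch-all assigns a value. The difficulty is that the value is one the record rules out.

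**Conclusion.** The rule is wrong as written. Whenever the month of last dose is known and the reference date falls in a later calendar year, the imputed date lies after the recorded month. This follows from the SAP text alone and needs no assumption.

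The practical effect is small. Under the stated assumptions (5–10% partial dates, 28-day lag, even spread over the year), about 0.14–0.28 participants are affected, with zero possible. One affected record with a 20–41 day excess would raise mean duration by 0.08–0.17 weeks over 34 participants, or by 0.95–1.95 weeks in the separately analysed group of 3. The study is descriptive and tests no hypothesis, so no inference changes. The point is minor but clear, and worth correcting because the error only ever lengthens exposure.

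**What to change.** Reword the second rule so that it compares year and month jointly: impute the last day of the recorded month whenever year and month are known and that year-month comes before the year-month of the earlier of treatment-phase disposition and death. Leave the year-only rule and the catch-all as they are.

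November 2021 with a reference date of 10 January 2022 then gives 30 November 2021, and December 2021 with 20 January 2022 gives 31 December 2021. All other cases keep their present result. The cost is one line of SAP text and one condition in the derivation program.

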### **Missing or Partial Death Dates**

Not Applicable.

### **Date of Start of New Anti-cancer Therapy**

Not applicable.

### **AE Onset Date:**

The following imputation rules apply if the event is unique for a patient or it is the first of a series of similar events; otherwise, the AE Onset Date will not be imputed:

- If the AE Collection Date is not missing, is less than the Date of First Exposure to Treatment, and is less than the AE Stop Date, then AE Onset Date is set to the Date of AE Collection.
- If the Previous Visit Date is greater than the Date of First Exposure to Treatment and less than the AE Stop Date, the AE Start Date is set to the previous visit date.

- If the Date of First Exposure to Treatment is greater than the previous visit date and less than the AE Stop Date, the AE Onset Date is set to the Date of First Exposure to Treatment.
- Otherwise AE Onset Date is set to the AE Stop Date.

#### **AE Stop Date:**

Ongoing events will have the AE Stop Date set to one of the following values:

- Date of Death, if the patient died and a date of death exists.
- Maximum of (Withdraw date, AE Onset Date, AE Collection Date) if the patient withdrew from the study and a date of withdraw exists.
- Maximum of (AE Onset Date, Subject Summary Collection Date, AE Collection Date) if the Disposition CRF page for the long-term follow-up phase exists but a date of completion/discontinuation does not exist.
- Maximum of (Last Treatment Date, AE Onset Date) if no Disposition CRF page for the long-term follow-up phase exists.

Imputation will only occur if event is unique for the patient, or it is the last of a series of similar events; otherwise the Stop Date will not be imputed. Adverse Events are deemed similar if they have the same verbatim term.

Resolved events will have the AE Stop Date set to the maximum of the AE collection date and the AE Onset date.

#### **Other Missing or Partial Dates**

Imputation methods for other partial dates are as follows:

- If the day of the month is missing for a start date used in a calculation, the first day of the month will be used to replace the missing date.
- If both the day and month are missing for a start date, the first day of the year is used.
- For stop dates, the last day of the month, or last day of the year is used if the day or day and month are missing, respectively.
- If the date is completely missing, no imputation will be performed.

#### **5.3.2. Missing Toxicity Grade of Adverse Events**

During Study Treatment: If no toxicity grade is available or the grade is reported as unknown for an adverse event during the study treatment, then the event will be considered treatment emergent.

In summaries which present maximum toxicity grade, the maximum of non-missing grades will be displayed. Missing grade will only be displayed for cases where a patient reported only one event and the grade is missing.

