### **5.2.9. Analyses for Categorical Data**

Qualitative variables will be summarized by frequency counts and percentages. Unless otherwise specified, the calculation of proportions will include the missing category. Therefore counts of missing observations will be included in the denominator and presented as a separate category.

In case the analysis refers only to certain visits, percentages will be based on the number of patients with an assessment at that visit, unless otherwise specified.

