## **5.3. Methods to Manage Missing Data**

Unless otherwise specified, all data will be evaluated as observed, and no imputation method for missing values will be used.

Any imputations will occur at the analysis dataset level. Additionally, in all patient data listings imputed values will be presented and flagged as imputed.

Missing statistics, eg, when they cannot be calculated, should be presented as 'ND' for not done, 'NR' for not reached or 'NA' for not applicable. For example, if N=1, the measure of variability cannot be computed and should be presented as 'ND' or 'NA'.

CDISC Safety Rulebook will be followed when handling the missing/partial dates, treatment emergent AE algorithm, missing AE grades, etc.

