### **6.3.1. Adverse Events**

All analyses will be based on treatment emergent events unless otherwise specified. Treatment emergent is defined in [Section 3.3.1](#).

Seriousness, toxicity grade, study drug action taken (interruption, reduction, and withdraw) are as reported by the investigator on the adverse event CRF.

Summaries by treatment arm, SOC and PT in decreasing frequency based on the frequencies observed in the glasdegib arm will be provided for:

- Treatment Emergent Events by Maximum Toxicity Grade (All Causality);
- Treatment Emergent Events by Maximum Toxicity Grade (Treatment Related); Serious Treatment Emergent Events by Maximum Toxicity Grade (All Causality);
- Serious Treatment Emergent Events by Maximum Toxicity Grade (Treatment Related).

An event will be considered treatment related if the investigator considered the event related to the study drug or this information is unknown.

- Treatment Emergent Adverse Events Leading to Dose Interruptions by Maximum Toxicity Grade (All Causality) separately for each study drug, for chemotherapy, and for any study treatment;
- Treatment Emergent Adverse Events Leading to Dose Reductions by Maximum Toxicity Grade (All Causality) separately for each study drug, for chemotherapy, and for any study treatment;
- Treatment Emergent Adverse Events Leading to Permanent Withdrawal by Maximum Toxicity Grade (All Causality) separately for each study drug, for chemotherapy, and for any study treatment;
- Serious Treatment Emergent Events (All Causality).

Each patient will be counted only once within each PT.

As described in [Section 5.3.2](#), in case a patient has events with missing and non-missing toxicity grades, the maximum of the non-missing grade will be displayed. Missing grade will only be displayed in the event that only one event has been reported for a patient and the grade is missing.

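### The missing-grade rule is set per patient but the maximum-grade AE tables are built per row, so some participants with an ungraded event have no permitted grade category

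*SAP*

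**What the plan says.** SAP 5.3.2 deals with events that have no grade or an unknown grade. If such an event occurs during study treatment, "then the event will be considered treatment emergent", so it belongs in the treatment-emergent tables. For display, the section says "In summaries which present maximum toxicity grade, the maximum of non-missing grades will be displayed", and then "Missing grade will only be displayed for cases where a patient reported only one event and the grade is missing".

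SAP 6.3.1 repeats the restriction in nearly the same words: "Missing grade will only be displayed in the event that only one event has been reported for a patient and the grade is missing". Neither sentence limits the single-event condition to a PT, an SOC or a particular table.

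The same section sets the layout: "Summaries by treatment arm, SOC and PT in decreasing frequency". The counting unit is "Each patient will be counted only once within each PT". Seven of the eight summaries listed there are by maximum grade: all-causality, treatment-related, serious all-causality, serious treatment-related, and events leading to interruption, reduction and withdrawal. The eighth, serious events of all causality, is not by grade. Nor are the three basic-results tables in SAP 6.3.1.1.

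Two general provisions also bear on the point. SAP 5.2.9 says of missing categorical data that "counts of missing observations will be included in the denominator and presented as a separate category", but only where no other section provides differently. SAP 5.3 adds: "CDISC Safety Rulebook will be followed when handling the missing/partial dates, treatment emergent AE algorithm, missing AE grades, etc". The content of that rulebook is not in the documents.

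**The concern.** The display condition looks at everything a participant reported, while each table cell describes one participant in one row. Take a participant with Grade 2 nausea and one ungraded pneumonia. In the pneumonia row there is no non-missing grade to show. The missing grade may not be shown either, because the participant reported two events. No grade category is left.

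Adverse events and serious adverse events are the only endpoint of the continuation study (Protocol Section 3), and worst grade is a stated basis for summarising them (Protocol 9.4.1, SAP Section 6). If programmers follow the text, the grade columns of a row may not add up to the number of participants with the event. The serious maximum-grade table may then disagree with the serious table without grades in the same section. Two programmers who read the condition differently could also produce different tables from the same data.

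**Working it through.** No hypothesis is tested and the plan gives no figure for this point, so there is nothing to reproduce. The check applies the written rule to a small set of illustrative records.

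**Inputs**
- Display rule: SAP 5.3.2 and 6.3.1.
- Row structure and once-per-PT counting: SAP 6.3.1.
- Participant numbers: at most 34 from B1371019 and 3 from B1371012, analysed separately (SAP 2.2 and Section 4).
- Arm sizes are not given. An even split, 34/2 = 17, is an assumption.

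**Step 1. Row for a term A under three readings**

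Literal means one event per patient. Per PT means one event per patient within the PT. Row-level means Missing whenever the patient has no graded event in the row.

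| Participant's events | Literal | Per PT | Row-level |
|---|---|---|---|
| A ungraded, nothing else | Missing | Missing | Missing |
| A ungraded; B Grade 2 | no category | Missing | Missing |
| A ungraded; A Grade 2 | Grade 2 | Grade 2 | Grade 2 |
| A ungraded twice | no category | no category | Missing |
| Placed in a category | 2 of 4 | 3 of 4 | 4 of 4 |

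The third participant stays in the row at Grade 2 under every reading. The per-PT reading repairs the second case but not the fourth.

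**Step 2. How often the literal condition would block a Missing cell**

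Assume that the number of other events in a participant with an ungraded event is Poisson with mean m. The ungraded event is the only one with probability exp(−m), so the share not eligible for a Missing cell is 1 − exp(−m).

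| m | 1 − exp(−m) |
|---|---|
| 0.5 | 39% |
| 1 | 63% |
| 2 | 86% |
| 3 | 95% |
| 5 | 99% |

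These are shares of the ungraded events, not of all events. Some of them sit beside a graded event of the same PT and do no harm. The table shows only that, on the literal reading, the single-event condition would seldom be met when participants report several events each.

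**Step 3. Weight of one affected participant**
- All B1371019 participants: 1/34 = 2.9%.
- Assumed arm: 1/17 = 5.9%.
- B1371012: 1/3 = 33.3%.

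The documents do not say how many events will lack a grade, so these figures cannot be turned into an expected undercount.

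**The case against.** A reader might infer that an ungraded event in anyone with other events vanishes from every maximum-grade table. The documents do not support that. A graded event in the same PT, in the same SOC, or anywhere for an any-event row keeps the participant in that row, as in any maximum-grade table.

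The strongest reply goes further. The two sentences govern which grade is displayed, not who is counted. The ungraded event is declared treatment emergent, the tables report the frequency of participants with such events, and each participant is counted once within each PT. Together these suggest that the participant stays in the row total and loses only a grade cell. The condition in 6.3.1 also closely follows the once-per-PT sentence, so a per-PT reading is natural and would settle the nausea and pneumonia example. This stands in part: a lower row total is a possibility, not something the SAP states. It does not settle the case of repeated ungraded events of one PT, which fails on either reading.

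A reader might also see a contradiction with SAP 5.2.9. There is none. That default yields to more specific provisions, and 5.3.2 is one. It is a departure from the default, and no reason is given for it.

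The cited rulebook may hold a row-level rule. That cannot be checked, and explicit SAP text written twice should not depend on an outside document to correct it.

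Finally, the practical effect may be nil. Protocol Appendix 3 (10.3.3) requires the investigator to grade every event, and Protocol 10.1.6 provides for source data verification. Serious events without a grade would still appear in the tables that ignore grade. All of this stands, and it limits the importance of the point.

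**Conclusion.** The rule as written does not fit the tables it governs. On the literal reading, a participant whose only event in a PT is ungraded and who has any other event has no permitted category in that row. On the per-PT reading, this is still true of a participant with two or more ungraded events of that PT. Such participants may be undercounted in the seven maximum-grade summaries, and those summaries may not reconcile with the serious-event and basic-results tables that are not by grade.

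One affected participant is 2.9% of 34, 5.9% of an assumed arm of 17, or 33.3% of 3. The 34 and 3 are maxima, so one participant weighs more if fewer enter. How many participants are affected depends on the number of ungraded events, which is unknown and may be zero. Certain loss of participants from the tables cannot be claimed, because the SAP is silent on the row total. This is a small defect in a descriptive analysis. It is worth correcting because adverse events are all that this study reports and the correction has no analytic downside.

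**What to change.** In SAP 5.3.2 and 6.3.1, replace the single-event condition with a rule applied separately to each PT row, each SOC row and any overall row:

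- Show the participant's maximum non-missing grade among the events in that row.
- If all of the participant's events in that row are ungraded, count the participant once under Missing.
- Include participants counted as Missing in the row total.

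This is also consistent with the 5.2.9 default and allows the tables with and without grade to be reconciled. The cost is two SAP sentences and one programming condition, with no new data collection.
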